- Following training: send out T5 surveys, payment, and relevant information for RETI participants

RANDOMIZATION

Providers and student random assignments occurred at the school level, with one provider per school recruited for the first year, and multiple people per school building was recruited for year two and three. We use this strategy to minimize analytic difficulties associated with reliably partitioning school and provider variance with small numbers of providers per school. Providers and TF-CBT trainers/consultants would be blinded to their BASIS condition assignment. To ensure comparability of conditions at baseline, minimize potential confounding, and maximize accuracy of effect estimates, we used a blocked randomization design. Schools were first blocked by state (WA, MN, IN, KY, WI, VT, PA, AZ, and MD) and district. We collected baseline provider data on implementation intentions and TPB and HAPA mechanisms (e.g., attitudes, norms, self-efficacy), identify matched pairs using these variables, and randomly assign providers within pairs to condition. Students were placed into TF-CBT or RETI based on the condition into which their school's existing SMH provider was randomized.

SECTION THREE: RECRUITMENT AND CONSENTING

SCHOOL DISTRICT

Participating schools (n=133) are located across multiple states. Schools are situated in diverse settings, including rural (n=1), suburban (n=2), and urban (n=2) regions and have total enrollments of 9,658 - 37,971 students. Student populations are diverse overall, with a mean of 44% of students identifying as racial/ethnic minorities (range 30% to 60%)

PROVIDER

Provider participants include 191 school mental health providers who were consented and randomized, but only 146 completed the BASIS+TF-CBT, AC+TF-CBT, RETI training to continue in the study. Provider recruitment across all three waves will occur with the assistance of district administrators. Principals will provide us with the email addresses of school mental health providers for recruitment.

1. Provider SCREENING CRITERIA

In order of preference:

1. Dedicated mental health providers that have regular individual psychotherapy sessions

- a. The school employed favorable over CBO (Community Based Organization), but CBO is a close second
2. People who devote some, but not all of their time to direct service delivery with students (e.g., pulling kids out and doing interventions), like...
 - a. School Social Worker;

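### The unit of assignment is given two ways that agree only in year 1, and the Aim 2b adoption analyses name no school, block or pair term, so the test may be mildly liberal or conservative

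*Combined protocol and SAP*

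**What the plan says.** The Randomization section contains both descriptions. It opens with "Providers and student random assignments occurred at the school level, with one provider per school recruited for the first year" and adds that "multiple people per school building was recruited for year two and three". It gives as the reason a wish to "minimize analytic difficulties associated with reliably partitioning school and provider variance with small numbers of providers per school". It then says "we used a blocked randomization design", that "Schools were first blocked by state" and district, and that the team would use baseline intentions and mechanism scores to form matched pairs and "randomly assign providers within pairs to condition". Students follow the condition of their school's provider, in the singular.

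Study Design (Section One), Conditions Overview and the pre-training task list (Section Two) describe providers as randomized. Section Three reports 133 schools and "191 school mental health providers who were consented and randomized", of whom 146 completed training. Study Design gives 158 providers.

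Section Six names Aim 1b and Aim 2b as the main analyses. For adoption, Aim 2b lists a cross tabulation and a survival analysis of BASIS against attention control (AC). Missing adoption counts as 0, and a sensitivity analysis excludes it. The Aim 1a, 1b and 2a entries each have a line on nesting, although none names school. The adoption entries have no such line and name no block, pair or clustering method.

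**The concern.** With one provider per school, assigning the school and assigning the provider are the same act. From year 2 they are not, and no rule says whether two providers in one building shared a condition. The stated reason for the design, avoiding a split of school and provider variance, fits year 1 only.

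The adoption comparison is made between providers, and its error rate depends on which description is true:

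- **Schools assigned, school ignored.** Colleagues in one building are likely to be alike in adoption, so provider-level standard errors may be too small. Leaving out the state/district blocks works the other way and can offset this.
- **Providers assigned within matched pairs, pairs ignored.** Standard errors are too large. The test is conservative, and the power that matching was meant to buy is lost.

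At stake is how to read a main result. A borderline finding could be slightly overstated, or a real effect of BASIS missed, and the document does not let a reader tell which.

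**Working it through.** The plan gives no significance level, power, intraclass correlation (ICC), adoption rate or sample-size calculation for Aim 2b, so there is no figure to reproduce. I assume a two-sided 5% test and show ranges.

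**Inputs from the documents:** 133 schools; 191 providers randomized; 146 trained. Providers per school averages 191/133 = 1.44 or 146/133 = 1.10.

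**Assumed:** ICC or within-pair correlation 0.05 to 0.30; schools have either one provider or a fixed larger number (2 or 4, with one odd-sized school where the count does not divide); 133 schools for both provider counts, an assumption tested below.

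**1. Schools assigned, school ignored, no benefit of blocking**

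Design effect DE = 1 + (Σm²/Σm − 1) × ICC, where m is providers per school. Actual error rate = 2 × [1 − Φ(1.96/√DE)].

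| Providers | Size of multi-provider schools | Σm²/Σm | ICC 0.05 | ICC 0.10 | ICC 0.30 |
|---|---|---|---|---|---|
| 191 | 2 | 307/191 = 1.607 | 5.35% | 5.7% | 7.1% |
| 191 | 4 | 421/191 = 2.204 | 5.7% | 6.4% | 9.3% |
| 146 | 2 | 172/146 = 1.178 | 5.1% | 5.2% | 5.6% |
| 146 | 4 | 196/146 = 1.342 | 5.2% | 5.4% | 6.2% |

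Example, top of the range: DE = 1 + 1.204 × 0.30 = 1.361; √DE = 1.167; 1.96/1.167 = 1.680; error rate 9.3%.

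**2. How far the provider count matters**

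The documents do not say which provider count the 133 schools belong to. If schools fell in proportion to providers, 146 providers came from 133 × 146/191 ≈ 102 schools, and the same formula gives 5.35% to 9.3%, as for 191. If 133 schools go with the 146 trained, then 191 came from 133 × 191/146 ≈ 174 schools, and the formula gives 5.1% to 6.2%. The contrast between 191 and 146 can therefore vanish or reverse. Only the overall range of 5.1% to 9.3% is usable.

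**3. Schools assigned within blocks, blocks also ignored**

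This was simulated for an unadjusted chi-square test (assumed: adoption 35%, 89 BASIS and AC schools, 127 or 97 providers, 9 or 18 blocks, ICC 0.05 to 0.30). With no school variance lying between blocks, the test ran at 5.1% to 8.9%. With half of it between blocks, it ran at 3.8% to 7.2%. Blocking can cancel the excess.

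**4. Providers assigned within pairs, pairs ignored**

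The true variance is (1 − ρ) times the one used, so the error rate = 2 × [1 − Φ(1.96/√(1 − ρ))].

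| ρ | 0.05 | 0.10 | 0.20 | 0.30 |
|---|---|---|---|---|
| Error rate | 4.4% | 3.9% | 2.8% | 1.9% |

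Simulations with 48 or 64 pairs and adoption of 35% or 40% agree: 4.4% to 4.7% at ρ = 0.05, and 1.9% to 2.1% at ρ = 0.30.

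**The case against.** The strongest reply has three parts.

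- **The contradiction is narrow.** Saying that providers were randomized, as Study Design, Conditions Overview and the pre-training list do, is ordinary wording when whole schools are assigned. A reader might count these as further contradictions, but they fit either reading. Blocking of schools and the placement of students by their school's provider lean towards the school as unit. The conflict is confined to the Randomization section and to years 2 and 3. This stands.
- **The effect is small in most cases.** With two providers per multi-provider school and an ICC of 0.05 to 0.10, the rate is 5.1% to 5.7%. The 9.3% needs an ICC of 0.30, four providers in essentially every multi-provider school, the higher ratio of providers to schools and no benefit of blocking, all at once. This also stands.
- **Section Six is an outline.** Silence about a term does not prove that the analysis left it out. That is fair. A reader might infer that the adoption test is inflated, or that a cluster trial was analysed as if individually randomized. The documents support neither: the unit is unsettled, and under the paired reading the error runs the other way.

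The reply does not reconcile the two statements, and nothing elsewhere in the documents does. The silence is also more than brevity, since other aims in the same table have a nesting line and the adoption entries have none.

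**Conclusion.** The point holds in a limited form. The Randomization section gives two units of assignment that agree only in year 1, and the adoption analyses of a main aim, as written, use neither the school nor the blocks and pairs.

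The consequence is uncertainty about direction more than a demonstrated bias: mildly liberal if schools were the units (about 5.1% to 9.3%, with the low end more plausible and blocking able to remove the excess), conservative if providers were assigned within pairs (about 4.4% down to 1.9%). These figures rest on assumed correlations, school sizes and a 5% level. The split between BASIS and AC is also not given. A reader might infer that the problem is worse for all 191 randomized than for the 146 trained, but that depends on an unstated number of schools and should not be relied on.

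Severity: minor to should-fix. The numerical effect is probably modest, but the unit of assignment is needed to interpret the result and is cheap to state.

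**What to change.** 1. **Reconcile the two statements.** Give the unit actually assigned in each year, say whether providers in one school always shared a condition, and explain how matched pairs were used with three conditions. Tabulate providers per school by year and arm, and say which provider count the 133 schools belong to.
2. **Match the adoption comparison to that unit.** If schools were assigned, use state/district block terms with school-clustered errors and a small-sample correction such as CR2. If providers were assigned within pairs, use a pair- or block-stratified test, or adjust for the baseline matching variables already collected. A re-randomisation test that repeats the actual allocation is valid in either case.
3. **Treat time to adoption in the same way.** Stratify by block or pair, or use a re-randomisation log-rank test. Use clustered robust errors only if schools were the units, and then with a small-sample correction. No survival model was simulated here, so this step rests on principle.

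The correction matters. In the simulated adoption comparisons, block terms with CR2 errors ran at 4.4% to 5.9% over ten settings, while block terms with ordinary clustered errors reached 7.1%.

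The cost is a paragraph, a table and modest extra programming. If schools were the units, intervals widen by up to about 17% (√1.361 = 1.167) in the most extreme assumed case, and by less elsewhere. If pairs or blocks were the units, using them should narrow the intervals.

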3. STUDY DESIGN

We conducted a hybrid type 2 effectiveness-implementation randomized trial. There was single provider from each participating school, for first cohort, then more than one provider after the first year (n=158) were randomized to BASIS plus TF-CBT (BASIS+TF-CBT), Attention Control plus TF-CBT (AC+TF-CBT), or Resource Efficient Treatment Intervention (RETI). **Aim 1** evaluated the main effects of TF-CBT on proximal mechanisms and clinical child outcomes, as well as test intervention mechanisms as mediators, moderators, and evaluate the cost-effectiveness of the intervention. **Aim 2** evaluated the main effects of BASIS on its mechanism of change and provider implementation outcomes, as well as test implementation mechanisms as mediators, moderators, and evaluated the cost-effectiveness of BASIS strategy. In addition, sequential mixed-methods data collection will explore how mechanisms are linked to implementation outcomes for "hypothesis defying residuals" (i.e., providers whose attitudes, subjective norms, and self-efficacy surrounding Evidence-Based Treatment (EBT) implementation are inconsistent with their documented implementation behaviors).

Project Timeline Overview (see Section 2.7 of Clinical Trials Information for fully detailed timeline)	Months 0-6 (Dec 2019- May 2020)	Months 6-12 (Jun 2020- Nov 2020)	Months 12-18 (Dec 2020- May 2021)	Months 18-24 (Jun 2021- Nov 2021)	Months 24-30 (Dec 2021- May 2022)	Months 30-36 (Jun 2022- Nov 2022)	Months 36-42 (Dec 2022- May 2023)	Months 42-48 (Jun 2023- Nov 2023)	Months 48-54 (Dec 2023- May 2024)	Months 54-60 (Jun 2024- Nov 2024)
Activities										
Clinician recruitment (n=120)		X		X		X				
Student recruitment (n=480)		X	X	X	X	X	X			
BASIS or Attention Control delivery		X		X		X				
TF-CBT or TAU delivery	X	X	X	X	X	X	X			
Clinician data collection	X	X	X	X	X	X	X	X		
Student data collection	X	X	X	X	X	X	X			
Aim 1 & 2 analyses							X	X		
Aim 1 & 2 manuscripts & dissemination							X	X	X	

SECTION TWO: INTERVENTION

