1. CONDITIONS OVERVIEW

Providers were randomized to one of two TF-CBT conditions or a RETI (Resource Efficient Trauma Intervention) condition. Those randomized to TF-CBT will receive either BASIS + TF-CBT or Attention control (AC) + TF-CBT. Both BASIS and AC bookend the TF-CBT 3-day training and will be followed by an online booster session. TF-CBT gold-standard training and 6 months of follow-up consultation were delivered by [name], [name], and [name].

Three Research Groups

BASIS plus TF-CBT (B + TF-CBT)

Providers in this research condition received the BASIS intervention prior to and post TF-CBT training.

Attention Control plus TF-CBT (AC + TF-CBT)

Providers in this research condition received attention control prior to and post TF-CBT training.

Resource-Efficient Trauma Intervention (RETI)

Providers in this research group received a half-day training and handout in RETI practices.

Clinical Interventions

RETI

Resource-Efficient Trauma Intervention (RETI) can be described as scaffold treatment-as-usual. It is a less prescriptive and resource-intensive intervention. It includes four core components – initial assessment, psychoeducation, social connection, and planning – which involve identifying which students have trauma exposure, connecting them to a practitioner who provides psychoeducation and social support, and the development of a support plan. This second approach provides school service providers with greater flexibility and autonomy but has been tested less extensively.

TF-CBT

TF-CBT was selected based on its established evidence and the stated need of participating districts to address student trauma and increasing concerns about student safety. TF-CBT is a 12-16 session intervention for students aged 3 to 18 years with trauma-exposure and related mental health sequelae. TF-CBT includes individual sessions for the youth, individual sessions for parents, and conjoint sessions that include involvement. The first third of TF-CBT focuses on psychoeducation and developing coping skills to reduce trauma-

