1. AC + TF-CBT

Providers randomly assigned to AC + TF-CBT will receive a 3-hour pre-training, 45-min post-training session, and an online booster 30-days post training to mirror the duration of BASIS and provide control providers with comparable amounts of attention. The in-person or virtual components of AC will be delivered by the same facilitator as BASIS ([name]) to control for facilitator effects. Content will be didactic, as in typical training for school mental health providers. The AC pre-training will provide content on the definition of Evidence-Based Treatment (EBT), how EBTs are established, why providers should use EBTs, clinical outcomes associated with different EBTs, and defining different dimensions of fidelity. The post-training session will involve having control providers reflect on TF-CBT, its core components, and discuss the outcomes associated with TF-CBT. The AC booster will prompt providers to reflect on and describe TF-CBT and identify and define each of its core components. The AC condition thus controls for dose, information provided, and interventionist effect.

1.2 Pre-Training Activities for internal teams:

2-4 Months Before Training (Ordinal Tasks must be completed in order; assumes dates have been set)

- Collect school demographics information

- Send Provider Baseline, give 1-2 weeks for completion
- Complete and ship goodie bags to district administrators
- Randomize Providers based on baseline and demographics information

1 Months Before Training

- Send Self-Paced Training link for those who are in TF-CBT
- Send out Zoom link and training calendar invites to /trainers
- Send reminder email for SPT link and reiterating dates for trainings

2 Weeks Before Training

- Check SPT completion rates, send reminders as needed
- Check-in with trainers
- Send out Zoom link and training calendar invites to participants/trainers

1 Week Before Training

- Reminder sent, links for training included
- T1 sent for completion
- Send YouTube training videos for research activities
- Friday before training – check for SPT completion and send reminders as needed

Training Day

- Send out Self-Paced Training gift cards for TF-CBT participants
- Check all T1 completion, send reminders to those who did not complete
- During training first 5 minutes: call on those who have not completed T1 to take time to complete T1
- Following training: send out T2 surveys to be completed by following morning for TF-CBT

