Youth participants (n=101), recruited by school mental health providers via their standard referral pathways (e.g., teacher - or self-referral; screening).

Inclusion

- Must meet TF-CBT eligibility criteria, including:

[figure not shown]
- Be within the TF-CBT developmental range (grades 3-12)
- Have traumatic event exposure
- Significant post-traumatic stress symptoms as indicated by a CPSS-V score ≥ 21

Exclusion

- Students with intellectual impairments or those who are not trauma exposed will be excluded
- Students (and caregivers at this time) must be English speaking

SCREENING CRITERIA

[figure not shown]
Providers will screen new cases for symptoms of trauma using a Trauma Screen (TS) and the Children PTSD Symptom Scale DSM-V (CPSS-5.) Once students are identified, providers will ask caregivers whether they are open to being contacted by the research team.

CONSENT/ASSENT AND ADMINISTRATION PROCESS

For caregivers who agree, contact information will be related to the team, who will follow up by phone to describe the research project, estimated time to participate, participant compensation, and obtain oral consent (a consent form will subsequently be mailed to

participants). For caregivers who consent, research staff will explain the study to students, answer questions, and obtain assent for participation. The procedures we used are based on prior collaboration with students on how best to communicate and approach obtaining assent.

SECTION FOUR: MEASURES AND DATA COLLECTION

[figure not shown]

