	Aim 1b: Evaluate main effects on child mental health outcomes (symptoms of PTSD, depression, anxiety) and test intervention mechanisms via a mediational model.	Multilevel Model 
Independent: RETI vs TF-CBTDependent: Child measured outcomes (CPSS-V (child and CG, SMFQ (child and CG))

		
 • Nesting: student under provider, time • Mediator: BASIS Mechanism (provider-level data) 
** There will be four different models- 1) base model with only intercept, 2) model with only IV, DV, and time, 3) model with IV, DV, time, and TF-CBT vs RETI interaction with time, and 4) lastly, IV, DV, and study group interaction (BASIS, AC, RETI) with time.

	Aim 1c: Evaluate the cost and cost-effectiveness of TF-CBT for improving clinical outcomes	

Main aim	Sub aim	Analysis method
Aim 2: Experimentally evaluate the impact of BASIS versus Attention Control (AC).	Aim 2a: Evaluate main effects on proximal implementation mechanisms of change (attitudes, subjective norms, self-efficacy, intentions to implement, and maintenance self-efficacy).	
Multilevel model
 
 • Independent (IV): AC vs BASIS • Dependent (DV): attitudes, subjective norms, self-efficacy, intentions • Nesting: Piecewise time (training, active, sustainment) • Interaction: Time X Study group 
 ◦ T1 to T5 X BASIS ◦ T6 to T9 X BASIS ◦ T10 to T12 X BASIS 
** There will be four different models- 1) model with only intercept, 2) model with only IV, DV, and time, 3) model with IV, DV, and study group interaction (BASIS, AC) with time, 4) 3) lastly, model with IV, DV, and study group interaction (BASIS, AC, and RETI) with time.

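### Aim 1b compares students of a post-randomisation subset of providers, retained after trainings of very different length by arm, without adjusting for the baseline provider scores used for matching

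*Combined protocol and SAP*

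**What the plan says.** **Counts.** Section Three (Provider) reports "191 school mental health providers who were consented and randomized", and then that "only 146 completed the BASIS+TF-CBT, AC+TF-CBT, RETI training to continue in the study". Section One (Study Design) gives another figure: "more than one provider after the first year (n=158) were randomized". Section Three (Student/Caregiver) reports "Youth participants (n=101), recruited by school mental health providers via their standard referral pathways".

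**Training by arm.** For RETI, Section Two (Conditions Overview) says: "Providers in this research group received a half-day training and handout in RETI practices". The TF-CBT arms have a required online course, a live training (three days in the Conditions Overview, two days in the later TF-CBT text), a session of about 3 hours before it, one of about 45 minutes after it, and an online booster at 30 days.

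**Timing and blinding.** Section Two, 1.2 (Pre-Training Activities) places the baseline survey and then randomisation 2 to 4 months before training. One month before training the staff task is "Send Self-Paced Training link for those who are in TF-CBT". Under Randomization, providers and trainers are blinded to the BASIS assignment; no blinding of TF-CBT against RETI is stated.

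**Baseline data.** Randomization says "We collected baseline provider data on implementation intentions and TPB and HAPA mechanisms". These scores defined the matched pairs, with the stated purpose of making the conditions comparable.

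**Analysis.** Section Six names Aim 1b as one of two main analyses. Its models contain arm, time, arm-by-time or group-by-time terms, and "Nesting: student under provider, time". The only other provider-level term is the BASIS mechanism, as a mediator. No provider baseline covariate, weighting, or sensitivity analysis for lost or non-contributing providers is listed.

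**The concern.** Randomisation balances all randomised providers. Aim 1b can use only those who passed two later steps: completing the arm's training, and having at least one student enrolled. The first step asks much more of a provider in the TF-CBT arms than in RETI, and providers could largely tell which of the two they had been given. If the steps retain different kinds of provider in the two conditions, the student comparison mixes the treatment effect with differences between providers. Losing one member of a matched pair also undoes the matching for that pair.

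Nothing in the Aim 1b models addresses this. Nesting handles correlation among students of one provider. A mediator measured after randomisation is not a baseline adjustment. The scores that could show or partly correct an imbalance are already held but do not enter the models. The plan describes Aim 1 as an experimental evaluation, so a reader would take the contrast as protected by randomisation.

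**Working it through.** **Inputs.** From Section Three: 191 randomised, 146 trained, 101 students. From Section One: 158 randomised. From Section Six: students are nested under providers, so I take one provider per student. The documents give no allocation ratio, losses by arm, ICC or number of contributing providers.

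**1. Loss before the end of training.** 146/191 = 76.4% completed; 191 − 146 = 45, and 45/191 = 23.6% did not. If 158 were randomised, the loss is 158 − 146 = 12, or 12/158 = 7.6%.

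**2. Providers without a student.** At most 101 providers can have one.

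| Denominator | Minimum with no student | Share |
|---|---|---|
| 191 randomised | 191 − 101 = 90 | 47.1% |
| 158 randomised | 158 − 101 = 57 | 36.1% |
| 146 trained | 146 − 101 = 45 | 30.8% |

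The last row does not depend on which randomised count is right. All three are floors, reached only if every contributing provider has exactly one student. At an assumed average of 2, 3 or 4 students, about 51, 34 or 26 providers contribute, and 140 (73%), 157 (82%) or 165 (86%) of 191 do not.

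**3. Range of loss by arm.** The 45 losses are not split. Two assumed allocations give:

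| Assumed TF-CBT : RETI | All 45 in TF-CBT | Near-even rates | All 45 in RETI |
|---|---|---|---|
| 127 : 64 (1:1:1 over three arms) | 45/127 = 35.4% vs 0% | 30/127 = 23.6% vs 15/64 = 23.4% | 0% vs 45/64 = 70.3% |
| 96 : 95 (1:1) | 45/96 = 46.9% vs 0% | 23/96 = 24.0% vs 22/95 = 23.2% | 0% vs 45/95 = 47.4% |

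The documents are compatible with every cell.

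**4. Illustration of a bias in outcome level.** Suppose each arm keeps the top share p of providers on a trait correlated r with the provider-level outcome. The bias in SD units is √ICC × r × (λ_TF-CBT − λ_RETI), with λ(p) = φ(z_p)/p. All inputs are assumed: ICC 0.05 to 0.15, r 0.3 to 0.5.

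- Shares 40% vs 75%: λ = 0.966 and 0.424, difference 0.542. Bias runs from 0.224 × 0.3 × 0.542 = 0.036 to 0.387 × 0.5 × 0.542 = 0.105.
- Shares 35% vs 89%: λ = 1.058 and 0.211, difference 0.847. Bias runs from 0.057 to 0.164.
- Equal shares: zero.

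On 127 : 64 these shares imply about 51 + 48 = 99 and 44 + 57 = 101 contributors, so both scenarios need about one student per provider. The formula gives a bias in mean level. It can apply to the arm main effect in Model 2. It does not carry over to the group-by-time terms of Models 3 and 4: a stable difference between providers would fall into the group main effect or the provider intercept. Biasing those terms requires selection related to student change from T6 to T8, and nothing in the documents sizes that.

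**The case against.** A reader might infer that the heavier TF-CBT training removed less motivated providers and so favours TF-CBT. The documents do not show this. They give training length, not losses by arm, timing or reason. The reverse is also plausible: TF-CBT providers receive a valued training, six months of consultation and payment for the online course, while RETI providers receive a half day and a handout. All entrants had agreed to give a year and to accept any of the three conditions. This objection stands, and the direction must be called unknown.

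Calling the contributing providers self-selected would also go too far. Under the student criteria and consent procedure, a provider may have no student because none reached the CPSS-V threshold, a caregiver declined, a student did not assent, or the language rule applied. That stands too.

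Against adjustment, the trial has been run and the Aim 2b entry already reports a fidelity result, so a covariate added now could be post hoc. If contributing providers number about 26, several covariates or within-arm weights would be unstable. Nor do the documents show that implementation scores predict student symptoms. These points limit the form of the remedy. They do not remove the gap: Aim 1b has no provision for the loss of whole providers, whereas Aim 2b has a rule and a sensitivity analysis for missing adoption data.

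**Conclusion.** The concern holds as a gap in the analysis and reporting of Aim 1b, not as a demonstrated bias. Retention depended on completing trainings of very different length, whichever of the two- and three-day texts is right. At least 47% of 191 randomised providers, or 36% of 158, contribute no student, assuming one provider per student. The models omit the baseline scores on which providers were matched. The size and direction of any bias are unknown because provider flow is not given by arm. The 0.04 to 0.16 SD illustration rests wholly on assumed inputs and bears at most on the Model 2 main effect; it should not be read as an estimate for Aim 1b as a whole. This is a change the sponsor should make, not one that invalidates the trial.

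**What to change.** 1. Add the pre-randomisation provider scores used for matching to Aim 1b as a provider-level covariate: intentions, or one small composite if few providers contribute. In Models 3 and 4 include its interaction with time, since a main effect alone would leave the group-by-time term largely unadjusted. Report it beside the unadjusted models, labelled post hoc if outcome data have been seen.
2. Report by arm, out of all randomised, how many providers completed training and how many contributed at least one student, with baseline scores of contributors and non-contributors. Reconcile 191 with 158, and the two- and three-day training texts.
3. If the shares or scores differ by arm, state the Aim 1b result as applying to providers who completed training and enrolled students, not as an unqualified experimental effect.
4. Treat inverse-probability weighting for contribution as exploratory only.

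The cost is SAP wording, a flow table and one further set of model runs on data already held, plus a few degrees of freedom. The Aim 1 conclusion may become narrower. Adjustment corrects only selection captured by the measured scores, so item 3 is still needed.

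### Students are recruited after randomisation by providers who know whether they deliver TF-CBT or RETI, and the Aim 1 models adjust for no student baseline characteristics, so differential recruitment can bias the contrast

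*Combined protocol and SAP*

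**What the plan says.** **Order of events.** The pre-training task list in Section Two places provider randomisation two to four months before training: "Randomize Providers based on baseline and demographics information". Under Randomization, students inherit the arm: "Students were placed into TF-CBT or RETI based on the condition into which" their school's provider was randomised.

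**Who finds the students.** Section Three (Student/Caregiver and Screening Criteria) gives this to the randomised providers. Students are "recruited by school mental health providers via their standard referral pathways". The providers also apply the Trauma Screen and the CPSS-5 to new cases, and ask caregivers whether the research team may contact them. Research staff come in after that step, to take consent and assent.

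**Who is blinded.** "Providers and TF-CBT trainers/consultants would be blinded to their BASIS condition assignment". Nothing comparable is stated for TF-CBT versus RETI. One task a month before training is "Send Self-Paced Training link for those who are in TF-CBT". For RETI, "Providers in this research group received a half-day training and handout in RETI practices".

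**The models.** Section Six calls Aims 1b and 2b the main analyses. Aims 1a and 1b each list four models:
- Model 1: intercept only.
- Model 2: "model with only IV, DV, and time".
- Model 3: adds TF-CBT versus RETI by time.
- Model 4: study group (BASIS, AC, RETI) by time.

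Students are nested in providers, and Aim 1b adds a provider-level mediator. No student covariate is named, and none of the four models is identified as supplying the effect estimate. Section Four (Student & Caregiver Measures) collects demographics and the symptom scales at T6, between the first and second appointments.

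**The concern.** Randomisation, with blocking by state and district and matching on provider survey scores, makes providers comparable. It does not make the students they later choose comparable.

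A provider trained in a 12-16 session therapy and one given a half-day training may reasonably put forward different students. The interventions themselves could also change who is found. Identifying trauma-exposed students is one of RETI's components, and the BASIS post-training session has providers plan with whom they will deliver TF-CBT.

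There is room for such differences. The timeline plans 480 students from 120 clinicians; Section Three reports 101 students and 146 providers who completed training.

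If severity or prognosis differs by arm at entry, a main analysis cannot separate the effect of TF-CBT from the effect of who was enrolled.

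**Working it through.** **Counts from the documents.** Planned yield is 480/120 = 4.0 students per clinician. Reported yield is 101/146 = 0.69 per trained provider. Students recruited are 101/480 = 21% of plan. These figures show room for selection. They do not show selection that differs by arm.

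**Assumptions, because the documents give no SD, correlation or student data by arm.** Three waves (T6, T7, T8); equal between-wave correlation r; a gap of d SD between arms at T6; no true treatment effect; clustering ignored. Group by time is read as the mean of T7 and T8 minus T6. Positive values mean more symptoms in the arm that recruits the more severe students.

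Two courses for the gap are compared. It may fade to rd at T7 and T8 (regression to the mean), or it may stay at d. With d = 0.3 and r = 0.6:

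| Estimate | Gap fades | Gap stable |
|---|---|---|
| Model 2 group coefficient | d(1+2r)/3 = 0.3 × 2.2/3 = 0.22 | d = 0.30 |
| Model 3 group by time | -d(1-r) = -0.3 × 0.4 = -0.12 | 0 |
| T7/T8 outcomes adjusted for T6 | 0 | d(1-r) = 0.3 × 0.4 = 0.12 |

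**Range for d = 0.2-0.5 and r = 0.3-0.7.** Model 2: 0.11 to 0.40 SD if the gap fades, 0.20 to 0.50 if stable. Group by time: -0.06 to -0.35 if it fades, 0 if stable. T6-adjusted: 0 if it fades, 0.06 to 0.35 if stable.

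**False-positive rates.** Simulation with 101 students split 1:1, d = 0.3, r = 0.5, nominal 5% two-sided test, 4000 runs. If the gap fades: about 22% (Model 2), 14% (group by time) and 5% (T6-adjusted). If stable: about 45%, 6% and 19%.

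**Which course is more plausible?** Providers select on their own screening, while T6 is a separate survey done by research staff. If selection acts on the screening score and that score correlates r with every later wave, a screening gap of 0.5 SD gives 0.6 × 0.5 = 0.30 SD at T6, T7 and T8 alike, which is the stable case. If it acts closer to the T6 score, the gap fades. The documents do not settle this.

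**What the pair of models can show.** The T6-adjusted estimate exceeds group by time by 0.12 SD in both columns (0 minus -0.12; 0.12 minus 0). Disagreement therefore signals a T6 gap, but not which model is right. If one arm instead recruits students likely to improve by 0.3 SD more, with no T6 gap, both estimates are off by about -0.3 SD and they agree.

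**Where T6 enters matters.** T6 is already an outcome wave. A T6 covariate added to Model 3 as a main effect shifts all waves equally and cancels from change, so the -0.12 is untouched. In Model 2 it would remove the 0.22, but that coefficient still averages over T6. A true effect of -0.50 SD at T7 and T8 appears as (0 - 0.50 - 0.50)/3 = -0.33, with or without the covariate.

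**The case against.** The strongest defence is that the plan already holds partial safeguards. The CPSS-V threshold of 21 applies in every arm, research staff take consent, and T6 is a wave of the repeated-measures model. Model 3 therefore handles a stable difference in level without any covariate, whereas adjusting for T6 would then introduce bias. That stands, and it is why adjustment should accompany the interaction and not replace it.

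It does not dispose of the point. The threshold is a floor, applied by the unblinded provider, and leaves severity above 21 and caregiver engagement free to differ. Consent by research staff comes after the provider's filter. Model 3 does not handle regression to the mean, or selection on prognosis.

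Three stronger readings are tempting and should be resisted:
- A reader might infer from 101 students and 146 providers that recruitment was selective by arm. Low overall yield is not evidence of that, and no counts or T6 scores by arm are given.
- A reader might take the models to hold group and time only. Models 3 and 4 include interactions with time, and the nesting is specified.
- A reader might conclude that T6 covariates cure the problem. The stable-gap column shows otherwise, and T6 falls after the first appointment, so it is not a clean pre-treatment baseline.

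**Conclusion.** The concern holds as a risk that the plan leaves unaddressed in a main analysis; it is not a demonstrated bias. Recruitment after randomisation by the randomised providers, and the absence of student covariates, are plain in the text. That providers know whether they deliver TF-CBT or RETI is inferred from the narrow blinding statement and the different training, but no other reading is workable.

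Under an assumed 0.3 SD gap and correlation of 0.6, the bias is 0.22 to 0.30 SD for the Model 2 coefficient and up to 0.12 SD in absolute size for either of the other two estimates, depending on whether the gap fades or persists. The actual size and direction cannot be known from the documents. The plan should be corrected, at small cost.

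**What to change.** 1. Do not use the Model 2 group coefficient as the effect estimate. Name group by time (Model 3) as the Aim 1 estimate, with grade band and a stated list of T6 demographics as covariates, and their interactions with time where they are meant to adjust change.
2. Report beside it a model with T7 and T8 only as outcomes, adjusted for the T6 value of the outcome, T6 CPSS-V, grade band and the same demographics. Treat disagreement between the two as a sign of sensitivity to selective recruitment, and do not treat agreement as proof of its absence.
3. Tabulate T6 characteristics and numbers enrolled by arm, plus numbers screened, eligible and approached where recorded. The documents describe no screening log, and contact details reach the team only for caregivers who agree, so some of these counts may not be recoverable.
4. State that Aim 1 rests on post-randomisation recruitment by providers not blinded to TF-CBT versus RETI, and that T6 follows the first appointment.
5. Parts of the document report completed work, so date the change and say whether Aim 1 results by arm had been seen.

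The cost is SAP wording, one extra model, a table and a few degrees of freedom with 101 students; the covariates are already collected. The T6-adjusted model is itself biased if the level gap is stable, and no analysis here removes unmeasured selection.
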